3.3 Sample Size Justification

Based on an alpha error of .05 and power of .80, with an absolute increase in LBR of 15% (consistent with earlier studies, and an overall LBR per transfer of 39.2% - from Society of Assisted Reproduction Technologies data) we will need to enroll 352 patients (176 in each group) to reach statistical significance. In order to account for attrition and the exclusion of patients moved to day 3 (earlier embryo transfer for poor embryo development), we will anticipate 20% dropout and plan to enroll 440 patients, 220 in each arm.

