4.2 Dependent Variables or Outcome Measures

Our primary outcome will be live birth rate per embryo transfer. The clinical pregnancy rate as well as the rate of twin gestation and OHSS (ovarian hyper-stimulation syndrome) will be secondary outcomes.

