4.4 Potential for Benefit

Studies in humans have shown that using Lupron increases pregnancy and live birth rates during IVF. The formulation and dose of Lupron used in this study is short acting and is metabolized and excreted from the body before implantation occurs.

5. Data Handling and Statistical Analysis

A computer-generated list of random numbers will be used for randomization. Patients will be randomized at the time of embryo transfer.

All databases will be de-identified. The identification key will be kept in a locked cabinet in the office of Genesis Fertility.

The study will take 2 years for recruitment and treatment, and 1 subsequent year for follow-up data collection (live birth status after treatment) and analysis.

Endpoints were listed above and are the gold standard for IVF experiments.

A univariate chi square analysis will be used to compare the two treatment groups with regard to percent of rate of live births in each group. Logistic regression will be used to compare rates in the treatment groups as a function of live transfer versus frozen embryo to determine any interaction effect due to type of transfer. Logistic regression will also be used to control for the possibility of any differences or confounding factors at baseline. A similar analysis plan will be used for the secondary outcomes.

6. Data and Safety Monitoring

Interim analyses will be performed after each 50 patients enrolled to ensure non-maleficance. Block analysis will ensure there is no bias at these interim analyses. We have a Data Safety and Monitoring Board who will be performing the block analyses.

Analysis will include assessment and statistical comparisons of clinical pregnancy rates, ongoing pregnancy rates, live birth rates, and any other complications, including hospitalizations, infections and miscarriage rate. Any significant difference in these outcomes at an interim analysis will trigger cessation of the study, and a complete report will be provided to the IRB that includes all clinical and research data collected in the study.

7. Reporting Results

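### Section 6 requires action on complications only when the arms differ significantly at a 50-patient look, which is insensitive to uncommon serious harms

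*Combined protocol and SAP*

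**What the plan says.** Section 6 (Data and Safety Monitoring) places a look after each 50 women enrolled, gives non-maleficence as the purpose, and assigns the analyses to a DSMB. The looks are to include assessment and statistical comparison of clinical pregnancy, ongoing pregnancy and live birth rates, and also of "any other complications, including hospitalizations, infections and miscarriage rate". One rule then covers the whole list: "Any significant difference in these outcomes at an interim analysis will trigger cessation of the study", followed by a full report to the IRB.

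Section 6 states no significance level, test or direction for this rule. Section 5 names chi-square for live birth and a similar approach for secondary outcomes; neither section names a test for complications at the looks. Ovarian hyperstimulation syndrome appears only in Section 4.2, where the twin gestation rate and "OHSS (ovarian hyper-stimulation syndrome) will be secondary outcomes"; Section 6 does not name it. Section 4.3 describes risks but attaches no monitoring action to them.

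**The concern.** A significance test can serve as a trigger for an outcome that happens in four women out of ten. It is a poor one for an outcome that happens in one or two women in a hundred, because the counts at each look are too small to reach .05 unless the imbalance is extreme. Section 6 applies the same trigger to both.

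At stake is the purpose the section sets for itself. If a serious complication were several times more frequent on Lupron, the protocol's one stated trigger might stay silent through many looks. The only IRB report that Section 6 mentions would stay silent with it, because it is tied to the same trigger.

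This differs from the false-positive problem of repeated unadjusted looks. The two pull in opposite directions: tightening the level to protect the live birth comparison would make the rule still less sensitive to rare harm. That is a reason to treat harm separately.

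**Working it through.** **1. Plan's own figures.** Section 3.3: "Based on an alpha error of .05 and power of .80", live birth 39.2% rising by 15 points to 54.2%. With a pooled-variance two-sided test and mean rate .467:

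n per arm = [1.960 × √(2 × .467 × .533) + 0.842 × √(.392 × .608 + .542 × .458)]² / .15² = (1.383 + 0.587)² / .0225 ≈ 172.5, so 173.

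The plan has 176, which is within 3%. 352 / 0.80 = 440, as stated ("we will anticipate 20% dropout and plan to enroll 440 patients, 220 in each arm"). The sample size reproduces, and nothing below depends on a fault in it.

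**2. Looks.** 440 / 50 = 8.8, so there are 8 looks, at 50, 100, …, 400 women. I take 25 per arm per step and read significant as two-sided p < .05. Both are assumptions.

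**3. Smallest imbalance that fires the rule: k events v 0, n per arm.** This step needs no event rate.

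- Uncorrected chi-square: X² = 2nk / (2n − k), to be compared with 3.841.
  - n = 25: k = 3 gives 150 / 47 = 3.19 (p = .074); k = 4 gives 200 / 46 = 4.35 (p = .037).
  - n = 200: k = 3 gives 1200 / 397 = 3.02 (p = .082); k = 4 gives 1600 / 396 = 4.04 (p = .044).
  - X² falls towards k as n grows, so 4 v 0 is needed at every look.
- Fisher, two-sided: p = 2 × C(n, k) / C(2n, k).
  - n = 25: k = 4 gives .110; k = 5 gives 2 × 53,130 / 2,118,760 = .0502; k = 6 gives .022.
  - n = 200: k = 5 gives .061; k = 6 gives .030. So 6 v 0 is needed at every look.
- With 1 event in one arm, the other needs 7 (chi-square) or 8 (Fisher) from 100 women on, and 6 or 7 at 50 women.

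**4. Chance that the rule has fired for harm.** The documents give no complication rates, so all rates here are assumed. I carried the joint distribution of cumulative counts through the looks. Each look adds Binomial(25, rate) to each arm, and a trial counts as stopped when Lupron has the excess and p < .05. One complication is considered alone, with complete outcomes at each look.

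| Control v Lupron | Expected Lupron events by 400 women (200 × rate) | Chi-square, by 200 / 400 | Fisher, by 200 / 400 |
|---|---|---|---|
| 0.5% v 2% | 4 | 9% / 31% | 1% / 11% |
| 1% v 3% | 6 | 17% / 37% | 4% / 20% |
| 1% v 4% | 8 | 29% / 58% | 10% / 41% |
| 0% v 3% | 6 | 35% / 85% | 8% / 56% |
| 2% v 8% | 16 | 56% / 87% | 40% / 79% |

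For a rate tripled from 1% to 3%, the rule has not fired in 100 − 37 = 63% of trials (chi-square) or 100 − 20 = 80% (Fisher) when 400 of 440 women are in.

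Complete outcomes is a favourable assumption. Looks are counted from enrolment, so the latest women will have little follow-up.

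**The case against.** The strongest objection is that Section 6 sets a mandatory stop and does not say that the DSMB may act only on significance. A reader might infer that the DSMB must stand by until p < .05, that a non-significant look amounts to permission to continue, or that no serious event can reach the DSMB between looks. The documents support none of these. The DSMB sees complications at every look, the stated purpose is to avoid harm, and the text is silent on expedited reporting. A short part of Section 3.4 was not in the text available, and no DSMB charter is among the documents. What stands is narrower: the available text describes no action on harm other than the significance trigger, no DSMB discretion and no between-look reporting.

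The second objection is that the percentages rest on assumed low rates and a single harm. That is fair. At 2% v 8% the chi-square rule fires in most trials. If two independent complications each ran at 1% v 4%, the chance that at least one fires is 1 − (1 − .29)² = 50% by 200 women and 1 − (1 − .58)² = 82% by 400. Miscarriage, also listed, need not be rare: at an assumed 15% v 30% the rule fires in 78% of trials by 200. So it would be wrong to say in general that harm goes unflagged through most of the trial. That description fits only low rates or modest excesses.

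Third, Fisher's test is not named in the plan. The chi-square column is closer to what Section 5 implies, and Fisher shows how far the answer moves when the test is left open.

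Finally, low power for rare events is inherent in a trial of 440, and judgement by a board has no calculable detection rate to set beside these figures. This is true, but it argues against making significance the only stated trigger for such events.

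**Conclusion.** The concern holds in a limited form. Section 6 contains no contradiction or arithmetical error. Its one stated trigger for complications serves the section's own aim poorly when events are uncommon.

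The firmest part needs no event rate: 3 v 0 by chi-square, or 5 v 0 by Fisher, requires no action at any look from 50 to 400 women. It rests only on reading significant as two-sided p < .05; a stricter interim level could only raise these counts.

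The size in practice is conditional. By 400 women the chi-square rule has fired for harm in 31% to 58% of trials when control risk is 0.5% to 1% and Lupron risk is three to four times that. It has fired in 87% at 2% v 8%. These figures assume equal arms at each look, complete outcomes and one complication alone. They describe when the protocol compels a stop. They do not describe when a DSMB using its own judgement would act.

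**What to change.** In Section 6, separate harm from efficacy and add wording to this effect:

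- Hospitalizations, serious infections and OHSS needing admission are forwarded to the DSMB as the site learns of them. Naming OHSS closes the gap between Sections 4.2 and 6.
- At each look the DSMB receives complication counts by arm, with risk differences and confidence intervals.
- Statistical significance is not required for the DSMB to recommend a pause or stop for harm.

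No numerical clinical threshold should be set. The statistical stopping rule for efficacy outcomes can then be specified separately, without its level limiting what the DSMB may do about harm.

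The cost is a paragraph in Section 6, a short event form and some extra time from a DSMB that already exists. No patients or visits are added. The downside is a small chance of a pause for events that prove unrelated.

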7.1 Individual Results

Subjects will be informed of their pregnancy status once the information is available, as is done for all patients. Patients will not be informed, even after the study, to which arm they had been randomized.

7.2 Aggregate Results

Our office website posts updates in “blog” format regarding news at the practice. All information regarding study outcomes can be posted in that forum, and patients/subjects are encouraged to check the website for updates.

